It is anticipated that all patients will be planned to receive 2 injections under this protocol, in order to allow dose-finding and to understand the duration of effect. Under certain circumstances a patient or investigator may decide to postpone or withhold the second dose. In general, if there appears to be any untoward safety risk, in situations including rapid deterioration of renal function, the development of uncontrolled diabetes, or the development of uncontrolled hypertension, or if there is the intercurrent development of a malignancy, the patient should not receive the second dose.

Second injections under this protocol will be staggered so that single injections in different patients occur no less than 3 weeks apart. The DSMB will review the clinical data regarding each of the first 3 second injections under this protocol, and will consult with the Sponsor before the 2nd, 3rd, and 4th second injections are made. Subsequent second injections will continue to be staggered so as to occur no less than 3 weeks apart, but individual DMSB review will not be required.

No staggering will be required for first NKA injections under this protocol.

Post-Injection Follow-up: Subjects will return to the clinic for follow-up safety assessments on Days 7, 14, and 28 post-injection and at 2, 3, and 6 months post-injection. At 6 months post-injection, post-treatment MRI and renal scintigraphy studies will be conducted. After patients complete the 6 month efficacy visit, they will be considered for a second NKA injection. Patients receiving a second dose will follow the same follow up visits that occurred after first injection. Patients 6 month post first injection visit will serve as the patients 14 to 10 day pre- second injection visit. Patients will return for their second injection and at 2, 3, and 6 months post-injection Patients will be followed up to 18 months in the post follow up phase with 6 months after first NKA injection and 12 months after second NKA injection. Refer to the time and events schedule on page 14 for additional post follow up time points.

Long Term Follow-up: Patients will be followed for safety and efficacy for 24 months after the 18 month initial follow up period. Telephone contact will be made 24 and 36 months after the last NKA injection, and visits will be made at 30 and 42 months after the last NKA injection.

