AE's ¹⁸		Χ	Х	Х	wee	Х	Х	Х	X	Х	Х	Х	Χ	Х	Х	Х	Х	Х	Х	Х	Х	Х	Х	Х	Х	Х	Х	Х	Χ	Χ																																															
ConMeds	Х	Χ	Х	Х	14 1	Х	Χ	Χ	X	Х	Х	Χ	Χ	Х	Х	Х	Х	Х	Х	Χ	Х	Х	Χ	Χ	Х	Х																																																			
KDQoL Survey ¹⁹					4	Х						Х		Х	Х						Х		Х	Х	Х	Х		Х		Х																																															

Time and Events	Schedule: New	Patients Re	eceiving Lapar	roscopic Approach
				 

¹ Screening assessments should be conducted within 45 days before the injection; if assessments fall outside of the 45 day window, rescreening should be conducted as discussed in Section 11.1

² If at 6 month visit the PI determines a second dose is not going to be completed patient should return to the clinic at month 9 visit and resume TES.

³ Monthly visit dates for long-term follow-up visits should be based on the calendar day (\pm 7 days).

⁴ Inpatient hospital days, Days 1 and possibly Days 2 and 3.

⁵ The patient will be discharged as early as Day 2 and as late as Day 4 following laparoscopic injection

⁶ Conduct End-of-Study (EOS) assessments at the 18 mo visit post second injection, or when the subject discontinues from the study (See Section 11.4)

⁷ The informed consent form (ICF) must be signed prior to conducting any study-specific procedures.

⁸ Appropriate selected Inclusion/Exclusion criteria should be reviewed at Screening, and pre-injection.

⁹ Medical and surgical history should be obtained at Screening.

 10 The physical examination (PE) is described in Section 12.2.2 .

¹¹ Vital signs include heart rate, resting BP, and body temperature. (See section 12.2.3)

¹² Vital signs should be measured throughout the procedure.

Confidential

¹³ An ultrasound should be performed 10 to 14 days before injection to verify continued eligibility and on Day 1 following injection to verify lack of adverse events/safety concerns.

¹⁴ If clinically indicated due to, for example, bleeding during the procedure or a drop in hemoglobin, an ultrasound may be performed prior to discharge to assess safety concerns.

¹⁵ To determine kidney size and volume, an MRI study should be performed between screening and the injection.

¹⁶ The patient may be released same day as biopsy per site standard practice, if released same day as biopsy skip day 1 procedures after biopsy.

¹⁷ NKA product should be handled and injected according to procedures described in the Study Reference Manual.

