10 STUDY POPULATION

10.1 Eligibility Criteria

Eligibility criteria should be assessed at Screening. In addition, unless otherwise noted for the specific criterion, eligibility criteria should be also be reviewed before the biopsy and at the Day -10 to -14 pre-injection visit.

Up to 30 subjects will be enrolled in this study, including subjects previously injected in either Phase 1 trial. Note that a subject will be considered enrolled into the study at the time of injection.

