14.3 Endpoints

The primary endpoint of the study is to assess the safety and efficacy of NKA injected in one recipient kidney and determine if two injections of NKA provide stabilization of renal function.

- Primary Safety Outcome Measures: procedure and/or product related adverse events (AE's) through 12 months following the initial NKA injection.
- Primary Efficacy Outcome Measures: serial measurement of serum creatinine and estimation of GFR through 6 months following the second cell injection

Secondary Endpoint

The secondary endpoint of the study is to assess the safety and tolerability of NKA administration by assessing renal-specific adverse events over a 12 month period following a patient's first NKA injection.

• Secondary Safety and Tolerability Outcome Measures: renal-specific laboratory assessments through 12 months following the last NKA injection under this protocol, whether first or second.

Exploratory Endpoints

The exploratory endpoint of the study are designed to assess the impact of NKA on renal function over a 12 month period following the initial NKA injection.

• Exploratory Outcome Measures: clinical diagnostic and laboratory assessments of renal structure and function (including eGFR, serum creatinine, and proteinuria) to assess changes in the rate of progression of renal disease; and effect of method of injection on these parameters.

Exploratory quality of life outcome measure will be the Kidney Disease Quality of Life survey obtained at baseline and at 1, 3, 6, 7, 9, 12, 15, 18, 30, and 42 months after a patient's first NKA injection.

- Changes from baseline in BUN, $_{\beta}2$ microglobulin and intact parathyroid hormone (iPTH) at 6 and 12 months post-injection.
- Changes from baseline in C-reactive protein (CRP) at 6 and 12 months post-injection.
- Need for initiation of renal replacement therapy.
- Comparison of pre-injection versus post-injection split functional differences between the left and right kidney based on renal scintigraphy.
- Comparison of pre-injection and post-injection kidney volume estimates based on comparative MRI assessments.
- Subgroup analyses will compare patients receiving a single injection with patients receiving two injections, and patients receiving laparoscopic injections with patients receiving percutaneous injections.

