14.4 Analysis Conventions

14.4.1 Analysis Sets

Full Analysis Set: The Full Analysis Set (FAS) will consist of all subjects who are enrolled in the study.

Injection Analysis Set: The Injection Analysis Set will include all patients who undergo a successful NKA injection.

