14.6 Efficacy Analysis

Not applicable.

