14.7.3 Laboratory Evaluations

Baseline values will be collected immediately prior to injection. Observed and change from baseline laboratory data will be summarized using a typical 8-number summary (sample size, mean, standard deviation, median, Q1, Q3, minimum, and maximum) for continuous variables and frequency and proportion for categorical variables. These summaries will be produced for both the FAS and the Injection analysis set. Generating inferential statistics is not planned.

Graded laboratory abnormalities will be defined using the NCI CTCAE grading scheme as defined in Section 12.3. Incidence of treatment-emergent laboratory abnormalities, defined as values that increase at least 1 toxicity grade from baseline at any time post baseline up to six months post-injection will be summarized. If baseline data are missing, then the latest value collected between biopsy and injection will be used as the baseline value. If baseline and pre-injection data are missing, then any graded abnormality, i.e., at least a Grade 1, will be considered treatment emergent.

Laboratory data summaries will be provided for both the FAS and the Injection analysis set. There are no plans to generate inferential statistics, except for variables concerning the rate of renal insufficiency progression. A paired t-test may be performed to assess the change in the rate of progression of renal insufficiency. Laboratory data will be provided in a data listing.

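### Stabilization of renal function is a primary question, but the plan commits to no comparison with the patient's own history, its declared control

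*Combined protocol and SAP*

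**What the plan says.** - **Objective and endpoint.** The Synopsis and sections 7.1, 14.2 and 14.3 make it primary to "determine if two injections of NKA provide stabilization of renal function". The efficacy measure is repeated creatinine and eGFR up to 6 months after the second injection.
- **Control.** The design is open-label with a single group. The Synopsis (Control Group) takes the patient's own history, covering at least 6 months, as comparator for the rate of progression.
- **Efficacy analysis.** Section 14.6 consists of "Not applicable".
- **Laboratory analysis.** Section 14.7.3, under Safety, states "Baseline values will be collected immediately prior to injection" and commits to descriptive summaries of observed values and changes from that baseline, in both analysis sets. It plans no inferential statistics, with an exception for rate-of-progression variables, and adds: "A paired t-test may be performed to assess the change in the rate of progression of renal insufficiency".
- **Other mentions.** Sections 7.2, 14.2 and 14.3 list change in the rate of progression among the exploratory measures. Section 14.8 commits to comparing one with two injections and laparoscopic with percutaneous injection.
- **Analysis sets.** The Full Analysis Set is all enrolled subjects (14.4.1), and section 10.1 says "Note that a subject will be considered enrolled into the study at the time of injection". "The Injection Analysis Set will include all patients who undergo a successful NKA injection".
- **Second dose.** The Synopsis foresees withholding it for safety risk, "in situations including rapid deterioration of renal function", and also for uncontrolled diabetes or hypertension or a malignancy. A patient or investigator may also decide against it. Footnote 2 of the Time and Events Schedules for new patients then says the "patient should return to the clinic at month 9 visit and resume TES".
- **Historical data.** Inclusion criterion 8 asks for two values at least 3 months apart within 12 months, enough data in consultation with the Medical Monitor, and a steady rate.

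**The concern.** The trial has no concurrent control, so the patient's previous slope is the only reference the plan declares for judging stabilization. The plan uses that reference only in an optional test. Two outcomes are then consistent with the protocol: no before/after rate comparison is reported, or one is reported whose windows, historical values, slope method and patients were chosen with the data in view. The word stabilization could likewise be given a meaning afterwards.

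The endpoint window adds a smaller gap. It ends 6 months after the second injection, so it is undefined for a patient who never has one. Since deterioration is one stated reason for not re-injecting, how those patients enter the comparison should be settled in advance.

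**Working it through.** **1. Which analyses use the declared control**

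| Analysis | Committed? | Uses the historical rate? |
|---|---|---|
| 14.6 Efficacy | None given | – |
| 14.7.3 descriptive change from baseline | Yes | No |
| 14.8 one vs two injections; injection route | Yes | No |
| 14.7.3 paired t-test on rate | Optional | Yes |
| 7.2/14.3 exploratory change in rate | Listed, no committed analysis | Implied |

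No row is both committed and clearly tied to the history.

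**2. Why change from baseline cannot stand in.** Take slopes in mL/min/1.73m² per year. Patient A goes from −6 before injection to −3 after; patient B is at −3 throughout. The 12-month change is −3 × 1 = −3 for both. The slope change is +3 for A and 0 for B. Even A has slowed, not necessarily stabilized, so a limit is needed.

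**3. What a committed estimate could deliver.** The plan has no figure to reproduce: up to 30 patients, no formal calculation. Assumptions, none from the documents: within-patient eGFR SD σ = 2 to 3; SD of true slope change 2 per year. If all 7 Phase 1 patients (6 Swedish, 1 US) return, 30 − 7 = 23 are new.

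Formulas: slope SE = σ/√Σ(t − t̄)². Half-width = t(0.975, n−1) × √(SE_pre² + SE_post² + 2²)/√n. Power is from the noncentral t, two-sided 5%, for a slope change of 4 per year.

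Pre-injection values are the history (last value taken 7 days before screening) plus screening, pre-biopsy, pre-injection and Day 0. Biopsy is 7 to 45 days after screening and injection 4 to 14 weeks after biopsy. Post-injection values are the scheduled visits through month 12 with two injections; SE_post = 1.90 to 2.84.

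Worked case (n = 23, two historical values 6 months apart):
- σ = 2, longest run-in: √(2.70² + 1.90² + 2²) = 3.86; 2.074 × 3.86/√23 = 1.67.
- σ = 3, shortest run-in: √(5.87² + 2.84² + 2²) = 6.82; 2.074 × 6.82/√23 = 2.95.

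| History | SE_pre | Half-width, n=30 | Power, n=30 | Half-width, n=23 | Power, n=23 |
|---|---|---|---|---|---|
| 2 values, 3 months | 3.6–10.4 | 1.69–4.08 | 49 to >99% | 1.95–4.72 | 39–98% |
| 2 values, 6 months | 2.7–5.9 | 1.44–2.55 | 87 to >99% | 1.67–2.95 | 77 to >99% |
| 3 values, 6 months | 2.5–5.5 | 1.39–2.43 | 90 to >99% | 1.61–2.81 | 80 to >99% |

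From two historical values alone, SE = σ√2/Δt, so a 3-month span doubles the SE of a 6-month span whatever σ is. The span gives the precision; a third value mainly lets steadiness be judged.

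**4. One-injection patients.** Followed at months 9 and 12 they have SE_post of 2.1 to 3.1. If 10 to 30% (assumed) of 23 are such patients, with three historical values over 6 months, keeping them leaves the half-width at 1.6 to 2.8; dropping them gives 1.7 to 3.5. In a simulation with no mean effect (slope mean −4, SD 3), dropping the 10, 20 or 30% with the worst observed change from Day 0 to month 6 made the mean slope change look better by about 0.3, 0.5–0.6 or 0.7–0.9 per year.

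**5. Returning patients.** n = 7, two values 6 months apart before the first injection, then visits from Day 0 to month 6 after the second: SE_pre = 5.7 to 8.5, SE_post = 4.6 to 6.9, half-width 7.0 to 10.3 per year. That supports description only.

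**The case against.** The strongest defence is that the plan is open about its aims. The Synopsis and 14.1 say that robust statistics and formal sizing are not intended in this Phase II study. Renal function will be reported, because 14.7.3 commits to laboratory summaries over time. The exception for rate variables shows that a rate analysis was in mind. All of this stands, and a reader who inferred that the plan has no analysis of renal function, or that the lack of a power calculation is an error, would go too far. It does not answer the point: a committed estimate with an interval needs no power claim, and optional wording leaves the declared control unused.

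Other stronger readings also fail:
- **One-injection patients are excluded, so the result is biased toward the product.** Nothing excludes them. Neither analysis set requires two injections, and the one-versus-two comparison is planned. The 0.3 to 0.9 effect is close to an upper bound: it assumes every patient not re-injected is among the worst at month 6, although the Synopsis gives other reasons. In the simulation only about 0.1 to 0.3 was a true slope difference among those kept; the rest was measurement noise.
- **The Synopsis and criterion 8 contradict each other.** Both can be met together, and criterion 8 adds Medical Monitor consultation. But a history can meet its 3-month floor and miss the Synopsis minimum, and two values cannot show a steady rate.
- **Returning patients will be compared with an already treated history.** The text does not say so. Previous history can include values from before NKA; section 6.3.4 says the Swedish study used the baseline rate as control, and part of the Phase 1 results was not in the text available to me. What stands is that the choice is not stated.
- **The analysis set is missing.** 14.7.3 applies both sets to laboratory summaries; it does not choose one for the rate comparison.

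**Conclusion.** The point holds on the text alone and should be fixed before data are analysed. A primary objective and endpoint rest on a comparison that the plan names as its control and then leaves optional, with stabilization undefined.

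The size is illustrative: under the assumed SDs, a committed estimate in 23 new patients with at least 6 months of history would have a 95% CI half-width of roughly 1.6 to 3.0 per year, useful for a Phase II decision without any formal power claim. The conclusion does not depend on those figures, on the assumed share of one-injection patients, or on the simulated selection effect. The one-injection window, the length of history and the returning patients' comparator are secondary matters of specification.

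**What to change.** 1. **Commit to one estimate.** Replace the entry in 14.6, and the optional wording in 14.7.3, with the within-patient change in eGFR slope from before the first NKA injection to the period ending 6 months after the second, with its 95% CI. Paired patient slopes or a random-slope model will do.
2. **Population.** All injected patients new to NKA, including those with one injection, using their available follow-up under footnote 2 (for example to month 12).
3. **Supporting analyses.** Patients with two injections only; the slope after the second injection alone (SE 4.6 to 6.9 per patient under the same assumptions, hence supporting); serum creatinine.
4. **Returning Phase 1 patients.** Report separately and descriptively, against values from before their first NKA injection where available.
5. **Stabilization.** Report the post-injection slope and its CI against a limit the sponsor fixes before data are seen.
6. **Laboratory comparability.** State when the site-laboratory re-analysis foreseen in 12.3 applies, so that historical and study values form one series.
7. **Secondary.** Reconcile the Synopsis minimum of 6 months with the 3-month floor in criterion 8 (Synopsis and 10.1.1).

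Cost: a protocol amendment with IRB/EC approval (15.1.1), some added site re-analysis, and longer histories for some candidates, which the Synopsis already requires. No new visits are needed.

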Randomization: Open-label, non-randomized.

Control Group: Each subject will serve as his or her own control; the patient's previous medical history, which must include a minimum 6 month period of observation of renal function, will serve as the comparator for rate of progression of renal insufficiency.

Sample Size: Up to 30 subjects will be injected with NKA. As this is a Phase II safety and efficacy study, robust statistical analysis will not be performed. Therefore, the sample size proposed for this study is a size typical for the active treatment group in Phase II studies, allowing for identification of safety outcomes and early efficacy in a limited population.

Study Population:

Male or female patients 30 to 70 years of age with Type 2 diabetes mellitus and CKD with eGFR between 20 and 50 mL/min/1.73m². An enrolled patient should have sufficient historical clinical data to determine his or her individual rate of CKD disease progression.

Inclusion Criteria: Unless otherwise noted, inclusion criteria must be met at Screening and prior to injection.

- 1. Male and female subjects, age 30 to 70 years on the date of informed consent.
- 2. Patients with type 2 diabetes mellitus (T2DM).
- 3. Patients with a well-established diagnosis of diabetic nephropathy as the underlying cause of their renal disease.
- At screening, patients not previously injected with NKA with CKD defined as a GFR of 20 50 mL/min/1.73m² inclusive. Patients previously treated with a single NKA injection with eGFR 15 to 60 mL/min may also enroll in this clinical trial.
- Microalbuminuria that cannot be explained by an alternative diagnosis. Microalbuminuria is defined as urinary albumin-creatinine ratio (UACR) ≥ 30 mg/g or urine albumin excretion ≥ 30 mg/day on 24 hour urine collection.
- 6. Prior to biopsy, systolic blood pressure between 105 and 140 mmHg (inclusive) and diastolic blood pressure ≤90 mmHg.
- 7. Ongoing and stable treatment with ACEI or ARB initiated at least 8 weeks prior to enrollment. Treatment must be stable for the 6 weeks immediately prior to injection. Stable treatment is defined as dose adjustment to no less than ½ of the current dosage and no more than 2X the current dosage over the 6 week period immediately prior to injection; dose interruptions of up to 7 days due to medical necessity are allowed. Patients who are intolerant to ACEI or ARBs may be included as long as they have stable BP within the acceptable limits.

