- 22. Patients with bleeding disorders that would, in the opinion of the Investigator, interfere with the performance of study procedures; patients taking coumarins (e.g. Warfarin) or other anticoagulants (e.g. enoxaparin or direct thrombin inhibitors).
- 23. Any circumstance in which the investigator deems participation in the study is not in the subject's best interest.
- 24. Use of any investigational product within 3 months of the injection without receiving prior written consent of the Medical Monitor.

Number of Sites: Up to 10 clinical centers will be included in the study.

Study Duration: 18 months NKA injections follow up followed by 24 month long term follow up for a total study duration of 42 months.

Study Enrollment: Up to 30 subjects undergoing NKA injection will be enrolled into the study. Patients who have received a single injection of NKA under previous research protocols may enroll in this clinical trial to receive a single additional injection. Patients who have never received an NKA injection may enroll in this clinical trial for up to a total of two (2) NKA injections, temporally spaced at least 6 months apart. All biopsies are to be taken from a single kidney, and all NKA injections are to be given into the kidney that was biopsied. Patients who complete screening procedures satisfying all I/E criteria will be enrolled into the study immediately prior to the injection. Patients who do not meet all criteria before injection will be considered screen failures. Once a patient has been injected, the patient will have completed treatment and every effort should be made to ensure the patient completes all follow-up visits. Injection dates for the first 3 patients receiving their second NKA injection will be staggered by a minimum of 3 week intervals to allow for assessment of acute adverse events and other safety parameters by the DSMB. Subsequent second injections will continue to be staggered so as to occur no less than 3 weeks apart, but individual DMSB review will not be required. At the completion of the follow-up visits, patients will continue in a long-term follow-up study. Patients will be followed for a total of 36 months following the last NKA injection under this protocol, whether the first or second injection.

Investigational Plan:

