10.1.1 Inclusion criteria

Unless otherwise noted, inclusion criteria must be met at Screening, Biopsy, and prior to injection.

- 1. Male and female subjects, age 30 to 70 years on the date of informed consent.
- 2. Patients with type 2 diabetes mellitus (T2DM).
- 3. Patients with a well-established diagnosis of diabetic nephropathy as the underlying cause of their renal disease.
- At screening, patients not previously injected with NKA with CKD defined as a GFR of 20 50 mL/min/1.73m² inclusive. Patients previously treated with a single NKA injection with eGFR 15 to 60 mL/min may also enroll in this clinical trial.
- 5. Microalbuminuria that cannot be explained by an alternative diagnosis. Microalbuminuria is defined as urinary albumin-creatinine ratio (UACR) \ge 30 mg/g or urine albumin excretion \ge 30 mg/day on 24 hour urine collection.
- 6. Prior to biopsy, systolic blood pressure between 105 and 140 mmHg (inclusive) and diastolic blood pressure ≤90 mmHg.
- 7. Ongoing and stable treatment with ACEI or ARB initiated at least 8 weeks prior to enrollment. Treatment must be stable for the 6 weeks immediately prior to injection. Stable treatment is defined as dose adjustment to no less than ½ of the current dosage and no more than 2X the current dosage over the 6 week period immediately prior to injection; dose interruptions of up to 7 days due to medical necessity are allowed. Patients who are intolerant to ACEI or ARBs may be included as long as they have stable BP within the acceptable limits.
- 8. Minimum of 2 measurements of eGFR or sCr taken at least 3 months apart (prior to screening) and within the previous 12 months to define the rate of progression of CKD. The patient should have sufficient historical data to provide a reasonable estimate of the rate of progression of CKD as determined following consultation with the Medical Monitor (to insure sufficient data is available). In addition, the rate of progression of CKD must be consistent over time. There is no defined rate of progression that is required to qualify for inclusion.
- 9. Willing and able to refrain from use of NSAIDs (including aspirin) and clopidogrel, prasugrel, or other platelet inhibitors peri-procedure (i.e., before and after both the biopsy and injection). The wash-out period before and after each procedure should be 7 days. Willing and able to refrain from use of fish oil and dipryridamole for 7 days before and 7 days after each procedure.

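### No planned analysis estimates whether renal function is stable after injection; the one named test, a paired t-test on the change in rate, speaks to slowing only

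*Combined protocol and SAP*

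**What the plan says.** Sections 7.1, 14.2 and 14.3 make it a primary aim to "determine if two injections of NKA provide stabilization of renal function". The primary efficacy outcome is "serial measurement of serum creatinine and estimation of GFR through 6 months following the second cell injection". Stabilization is given no numerical meaning: no slope, margin or responder rule.

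Section 14.6 (Efficacy Analysis) reads "Not applicable". The only inferential method named anywhere is in section 14.7.3, under Safety Analysis: "There are no plans to generate inferential statistics, except for variables concerning the rate of renal insufficiency progression", followed by "A paired t-test may be performed to assess the change in the rate of progression of renal insufficiency". No significance level, sidedness, slope definition or post-injection window is given. Otherwise eGFR and serum creatinine receive descriptive summaries only.

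The synopsis makes each patient's own history the control; it "will serve as the comparator for rate of progression of renal insufficiency". Inclusion criterion 8 asks for at least two eGFR or creatinine values at least 3 months apart within the previous 12 months, and adds: "There is no defined rate of progression that is required to qualify for inclusion". The synopsis also states that "all NKA injections are to be given into the kidney that was biopsied". Up to 30 patients are planned, with no formal sample size calculation.

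**The concern.** Whether function is stable is a question about the rate after injection: is it near zero, or at least no worse than some tolerated loss? The paired t-test asks whether the rate after injection differs from the rate before. The two answers can disagree in both directions.

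- **Slowed but still falling.** The paired test can be positive while patients go on losing function. Only one kidney is injected. If, as an illustration, each kidney carried half of total function and any effect stayed in the injected one, complete arrest there would only halve the overall decline. Neither condition is a figure in the documents.
- **Fully stable after a slow decline.** Criterion 8 admits slow progressors and patients who are already stable. They have little room to improve, so the paired test will seldom be positive even if function holds.

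At stake is the wording of the trial's efficacy conclusion. A significant paired result supports slowing. A non-significant one supports neither stability nor the absence of renal harm.

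**Working it through.** **Inputs.** From the documents: n up to 30; comparison with the patient's own earlier rate; minimum history of two values 3 months apart; primary outcome up to 6 months after the second injection. Assumed, because the documents give none of them: two-sided 0.05; within-patient eGFR SD 3 mL/min/1.73m²; between-patient slope SD 3 mL/min/1.73m²/yr; illustrative tolerated loss of 1 mL/min/1.73m²/yr. The plan has no power figure to reproduce. Rates below are in mL/min/1.73m²/yr.

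**1. When the paired test is positive.** With d = rate after minus rate before, t = mean(d) / (SD(d)/√n). At n = 30 the critical value is 2.045, so the test favours NKA when mean(d) > (2.045/√30) × SD(d) = 0.373 × SD(d). For SD(d) of 4, 6 or 8 the thresholds are 1.49, 2.24 and 2.99. The post-injection rate itself does not enter.

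**2. Worked case.** Mean rate −6 before and −3 after, SD(d) = 6, n = 30:
- t = 3/(6/√30) = 2.74, p = 0.010; 95% CI for the change 0.76 to 5.24.
- With a post-injection slope SD of 4, the 95% CI for the post-injection rate is −3 ± 2.045 × 4/√30 = −4.49 to −1.51.

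The test is positive, yet the whole interval for the current rate lies below zero.

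**3. How often, when decline is halved but continues (n = 30, simulated).** Per-patient least-squares slopes, then the paired test:

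| History | Post-injection data | Patient slope deviations before and after | −4 to −2 | −6 to −3 | −8 to −4 |
|---|---|---|---|---|---|
| 4 values over 12 months | 12 months | identical | 51% | 83% | 97% |
| 4 values over 12 months | 12 months | independent | about 35% | about 65% | about 88% |
| 4 values over 12 months | 6 months | identical | 24% | 46–48% | 71% |
| 2 values 6 months apart | 12 months | identical | 21% | (between) | 63% |
| 2 values 3 months apart | 12 months | either | 9% | (between) | 23% |

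The spread comes largely from measurement error in the historical slope, whose SD is 3/√Σ(t − t̄)²:
- four evenly spaced values over a year: 3/√0.556 = 4.0;
- two values 6 months apart: 3/√0.125 = 8.5;
- two values 3 months apart: 3/√0.03125 = 17.0.

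**4. The reverse case.** For a cohort going from −1 to 0, the paired test is positive in 26%, 14% or 10% of trials for SD(d) of 4, 6 or 8. In the slope simulation the figure is 5% to 17%, depending on the history. A cohort stable both before and after is positive in the favourable direction in 2.5%.

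**5. Looking at the post-injection slope directly.** Suppose stabilization requires the lower 95% bound of the mean post-injection slope to lie above −1 (n = 30, same SDs):
- halved-but-declining cohorts with 12 months of post-injection data: satisfied in 0.3% or fewer;
- truly stable cohorts (slope 0): satisfied in about 21% with 12 months of data and about 10% with 6 months.

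Also requiring a significant rate change would be a mistake. In the −1 to 0 cohort the joint rule is met in about 8% of trials, against 16–17% for the paired test alone.

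**6. Non-significance and harm.** A true worsening of 0.5 SD of the change is missed by the paired test in about 25% of trials at n = 30 and 44% at n = 20 (non-central t, non-centrality 0.5√n).

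**The case against.** The protocol never says that the paired test is its test of stabilization. The test sits under Safety Analysis, is optional, and fits other stated aims: the exploratory outcome on changes in the rate of progression, the choice of the patient's own history as control, and the rationale of slowing disease. The synopsis disclaims robust statistical analysis, and the change-from-baseline summaries would show continuing loss. If the sponsor means slowing when it writes stabilization, the test is the right one. The deeper gap is that the term is undefined.

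Most of this stands. A reader might infer that the plan tests a wrong null hypothesis and that the percentages in the table are false-positive rates to set against 2.5%. The documents do not support that. They write out no null, and in those scenarios the decline really has slowed, so the test is right about what it measures. Nor is this strictly the only inference possible: comparisons of one with two injections, and of the two injection routes, are planned without a named method. Nor does the point touch the safety part of the primary objective.

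The Phase 1 rate-of-decline figure and per-patient tables (Figure 5, Tables 3 and 4) were not in the text available to me, so observed slopes could not replace the assumed ones.

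What remains is that descriptive summaries carry no margin or decision rule, and that making the paired test mandatory would still not supply an estimate of the post-injection rate.

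**Conclusion.** The point holds in this form: the objective asks about stability after two injections, and no planned analysis estimates that quantity with its uncertainty. The named test addresses slowing against the patient's own history.

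The 0.373 SD threshold depends only on n = 30 and a two-sided 5% level. The 9% to 97% range rests on assumed SDs and rates, and its upper end needs four historical values, a full year of post-injection data and an identical shift in every patient's slope. It shows that the two questions can separate; it does not predict this trial's result. This is a cheap improvement, not a flaw that invalidates the study.

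**What to change.** In sections 14.6 and 14.7.3:

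1. Report the mean paired change in eGFR slope with a 95% CI and label it as evidence on slowing only.
2. Report the mean post-injection eGFR slope with a 95% CI over a window tied to the primary outcome, ending 6 months after the second injection. State where the window starts: starting at the first injection gives more data but mixes one- and two-injection periods. Use the word stabilization only if the lower bound lies above a tolerated loss that the sponsor fixes before data review. Do not also require a significant rate change. Present the pre-injection slope beside it, because patients who were already stable may enrol.
3. State that a non-significant paired test is evidence neither of stability nor of no renal harm.

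The cost is wording plus one estimate from data already collected. The downside is that the claim becomes hard to make with at most 30 patients: with the illustrative margin and a true slope of zero, about 21% with 12 months of post-injection data and about 10% with 6. The claim the trial is likely to be able to support is slowing.
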